2.4 SAMPLE SIZE

A sample size of 64 participants provides approximately 90% power to detect a treatment effect of at least 10mm, assuming a Type I error of 5%. Allowing for loss to follow-up of 40% of participants through the trial inflates the required sample size to 107 participants.

Period effects (changes in underlying VAS pain score due to factors other than randomised treatment, e.g. seasonal, activity-related, etc.), variability in individual statin effects across patients, and imperfect adherence to the assigned treatment were investigated by further detailed simulations. VAS pain scores are not normally distributed, since they are bounded (0-100mm) and can display large fluctuations in response. Therefore, further power calculations were performed drawing the outcome from a Beta distribution, and from a distribution with normal variance components on a logit scale, to assess the robustness of the sample size estimates to the distribution chosen. These factors all have the effect of decreasing power, thus increasing the sample size required. An approximate 80% increase in the sample size required in the absence of these effects provided approximately 90% or more power across a plausible range of these potential effects, thus we determined that a final sample size of 200 was required.

Multiple testing: Rather than making formal adjustments for multiple testing, we follow an approach advocated by Pocock²⁵ of clearly specifying our primary analysis (which provides a single test for treatment effect), while explicitly presenting and interpreting all other tests as secondary analyses.

Power for individual N-of-1 trials: In order to increase the statistical power for the analysis of individual N-of-1 trials, we will ask participants to report symptoms daily in the last week of each period, rather than once per period. Full adherence through the trial will provide between 55 and 70% power to detect effects of 10mm or greater for individual treatment comparisons.

Estimates of recruitment and retention rates: We anticipate that some patients will not complete data in each treatment period, and that some will not complete their 12-month follow-up. By designing this study as a series of N-of-1 trials, which offer individual participant benefit in the form of an individualised estimate of effect, we hope to minimise this type of dropout. However, we have accounted for this in our sample size calculation by allowing for 40% loss to follow-up.

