Appendix 3: StatinWISE End of Trial data form

End of Trial Form (Month 15) / Early Withdrawal

1. Did the patient complete 6 Treatment Periods?

YES

A.1. Has the Research Nurse/GP spoken to the patient to discuss their individual results?

(i) YES

(ia) Date seen: _____ dd/mm/yyyy

(ii) NO – (please arrange an appointment).

(iia) Date of appointment: _____ dd/mm/yyyy

A.2. Has the patient seen his/her GP since end of Treatment Period 6?

(i) YES

(ii) NO (please remind the patient to book an appointment)

(iia) Date reminder done: _____ dd/mm/yyyy

A.3. Has the patient been given a statin prescription in the 4 weeks since Treatment Period 6 ended?

(i) YES

(ia) Name of Statin: _____

(ib) Dose of statin: _____

(ii) NO

A.4. Has the patient found their own trial results helpful to reach the decision as to whether to continue statin use?

YES/NO

NO

B.1. Please tick reason why the patient did not complete 6 treatment periods:

Lost to follow-up

Early withdrawal

Death

B.2. Lost to follow-up:

Date of last contact with patient? _____

Dd/mm/yyyy

B.3. If Early withdrawal, give reason:

- a. withdrawal of informed consent
- b. intolerable muscle symptoms*
- c. clinical concern*
- d. other*

*: please enter details here: _____

B.4. Has the patient contacted their GP to discuss reason for withdrawal?

(i) YES

(ia) Date seen: _____ dd/mm/yyyy

(ii) NO – (advise patient to contact GP).

B.5. Has the Research Nurse/GP spoken to the patient to discuss their individual results?

(i) YES

(ia) Date seen: _____ dd/mm/yyyy

(ii) NO – (please arrange an appointment).

(iia) Date of appointment: _____ dd/mm/yyyy

B.6. Death (SAE report form must be completed)

B.6.a. Date of death: _____ dd/mm/yyyy

B.6.b Cause of death (either autopsy report or clinical judgement if autopsy not available):

B.6.c. Date SAE form completed: _____ dd/mm/yyyy

C.1. This form was completed by: _____ Date: dd/mm/yyyy

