Appendix 4: StatinWISE Patient questionnaire

INSTRUCTIONS

This questionnaire is to be filled out once every two months (on day 56). We will remind you one day before it is due. Please answer all questions. If you need any help to complete the form. Please call our Freephone number [name] or email the study team: [contact].

PART 1: ADHERENCE TO MEDICATION

Step 1 (all participants):

Q1. How would you best describe your use of study medication in the past two months? (Please choose one of the following options)

- I didn't take my study medication at all
- I took my study medication on some days
- I took my study medication on most days, but missed an occasional dose
- I took my study medications every day

Step 2 (appears if the participant chooses "I didn't take my study medication at all", or "I took my study medication on some days"):

Q2. What was the reason that you didn't take your study medication every day in the past two months? (please tick all that apply)

- I forgot to take my study medication

Ticking the above will prompt the following option, if ticked, the trial team will action:

- Would you like a daily reminder sent to you via email/push notification

- I was prescribed another medication and my doctor told me to stop taking my study medication

Ticking the above will prompt an alert for the trial team to contact surgery for details and consider withdrawal from study

- My doctor recommended that I stop taking study medication because of muscle symptoms

Ticking the above will prompt an alert for the trial team to contact surgery for details

- I decided to stop taking study medication because of muscle symptoms

Ticking the above will prompt an alert for the patient to contact the GP for advice

- I didn't want to take my study medication

Ticking the above will prompt the following option, if ticked NO, the trial team will arrange for end of trial:

Do you still wish to participate in the trial: Yes No

- Other (please specify)

(free text)

PART 2: EXPLORING SYMPTOMS IN THE PAST TWO MONTHS

1. *(all participants):* In the last two months, have you experienced muscle symptoms, e.g. muscle pain or weakness?

Yes
 No

2. *(appears if the participant ticks yes for Question 1):* Do you think these muscle symptoms are related to your study medication?

Yes
 No
 Don't know

[figure not shown]
3. *(appears if the participant ticks no for Question 2):* What do you think may have caused these muscle symptoms?
(free text)

Don't know

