1.8 DEFINITION OF SECONDARY OUTCOMES

The following secondary outcomes will be collected once at the end of each of the 6 treatment periods, via the patient questionnaire form (Appendix 2).

- Whether or not the patient experienced muscle symptoms that they believe were caused by the study medication (yes/no/don't know).
- Site of muscle symptoms:
 - Single/multiple
 - head and neck/upper limbs/lower limbs/trunk
- Visual Analogue Scale scores (range 0-10) for how the participant's muscle symptoms impact on the following:
 - General activity
 - Mood
 - Walking ability
 - Normal work (includes both work outside the home and housework)
 - Relations with other people
 - Sleep
 - Enjoyment of life

These are collected only if the participant reports muscle symptoms during that period. For comparisons between randomized treatments these VAS scores will be set to zero for participants who report no muscle symptoms in that period.

- Other symptoms that the patient believes can be attributed to the study medication. These will be entered as free text and grouped into: musculoskeletal/gastrointestinal/respiratory/neurological/psychological/other (not mutually exclusive categories).
- Adherence to study medication:
 - not at all/some days/most days/every day

Adherence will also be assessed in the following ways:

- number of pills remaining in returned packages (0-56; collected each treatment period)
- self-report ("took pill yesterday" - yes/no; collected daily during the last 7 days of each of the 6 treatment periods)

The final secondary outcomes will be collected in the end of trial interview with the participant:

- Participant decision regarding future statin use and the relationship to their primary outcome (patient has been given a statin prescription in 4 weeks following trial - yes/no).
- Whether patients found their own trial result helpful in making the decision about future statin use (yes/no).

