1.9 DEFINITION OF THE SAFETY VARIABLES

- Occurrence of adverse event
- Occurrence of serious adverse event

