1.10 ANALYSIS PRINCIPLES FOR FINAL ANALYSIS

- All analyses will be conducted on an ‘intention-to-treat’ basis, defined as follows:
 - All patients who enter at least one VAS score for muscle symptoms during a statin period and at least one VAS score for muscle symptoms during a placebo period will be included in the final primary analysis.
 - For analyses of secondary outcomes from the patient questionnaire (single monthly measurement), analyses will include all patients who complete at least one measure during a statin period and at least one measure during a placebo period.
 - Periods of allocation to statin will be compared to periods of allocation to placebo, irrespective of adherence to the allocated treatment.
- All statistical tests will be two-sided, and the nominal level of α will be 5%. Confidence intervals for the primary outcome will be set at the 95% level.
- P values will not be adjusted for multiplicity. However, the outcomes are clearly categorised by degree of importance (primary and secondary). Confidence intervals for secondary outcomes will be set at the 99% level.
- The primary analysis will not impute missing values. Where the number of missing observations is substantial, we will report the number of observations used in the analysis. Robustness of conclusions to missing data will be explored via sensitivity analysis.
- Analyses exploring the effect of adherence on primary and secondary outcomes will be undertaken as secondary analyses.
- All adverse events will be coded using MedDRA Version 19.1.

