2.3.7 SECONDARY ANALYSES

Withdrawal, Loss to follow-up and Adherence – Descriptive analyses

Loss to follow up and withdrawal, with reasons for withdrawal, will be summarized by overall frequencies and percentages. Protocol violations will be tabulated. Descriptive statistics, including graphical summaries, will be used to summarise the measures of adherence to randomized treatment and withdrawal, and their relationship to the statin and placebo periods.

Withdrawal – Comparison between statin and placebo periods

We will explore whether the period in which a patient was first known to have withdrawn was more likely to have been a placebo or a statin period. If this date is after the end of a treatment period but the patient chooses not to begin the next period, the period in which the withdrawal happens will be set to the period just ended.

Adherence – Randomised comparison

We will explore whether adherence was lower on statin periods compared with placebo periods using mixed models similar to those described above.

Adherence – Efficacy analyses

We will use the measures of adherence to randomised treatment to perform an efficacy analysis based around an instrumental variables approach. Because these analyses require much stronger assumptions than the intention-to-treat analysis above, the results of the efficacy analysis will be presented and interpreted as a secondary analysis.

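### Withdrawal or stopping because of muscle symptoms is recorded, but SAP 2.3.7 never compares it between statin and placebo; a reason-by-treatment table and one pre-specified estimate would close the gap cheaply

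*SAP*

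**What the plan says.** **What is recorded.** In Protocol Appendix 3 (End of Trial form), item B.1 separates loss to follow-up, early withdrawal and death. For early withdrawal, item B.3 offers four reasons, one of which is "b. intolerable muscle symptoms". In Protocol Appendix 4 (Patient questionnaire, Part 1), Q2 asks each period why study medication was not taken. One option is "I decided to stop taking study medication because of muscle symptoms", and another covers stopping for muscle symptoms on a doctor's recommendation.

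**What is analysed.** SAP 2.3.7 deals with reasons in one sentence: "Loss to follow up and withdrawal, with reasons for withdrawal, will be summarized by overall frequencies and percentages". It then plans:

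- descriptive summaries of adherence and withdrawal in relation to statin and placebo periods;
- an exploration of whether the period of first known withdrawal "was more likely to have been a placebo or a statin period";
- mixed models asking whether adherence was lower on statin.

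None of these mentions the reason. SAP 1.8 defines adherence by the four-category answer ("not at all/some days/most days/every day"), by returned pill counts and by a daily yes/no item, again without the reason. The safety variables in SAP 1.9 begin with "Occurrence of adverse event" and add serious adverse events; SAP 2.3.3 tabulates these and SUSARs by allocated treatment.

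**The concern.** Patients enter this trial because they have stopped a statin, or are thinking of stopping, on account of muscle symptoms. Whether, under blinding, they stop for that reason more often on statin than on placebo is close to the trial's own question. Followed as written, the report would give one overall count of muscle-symptom withdrawals and an all-cause comparison in which withdrawals for other reasons are mixed in. If those are balanced between treatments, they pull any real difference towards none.

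The primary analysis does not fully cover the same ground. SAP 1.10 requires at least one VAS score in a statin period and one in a placebo period. Treatments are paired within periods 1-2, 3-4 and 5-6 (Protocol 2.8), so a patient who leaves for symptoms in period 1, or in period 2 before any VAS entry, has data on one treatment at most and is excluded. For such patients the recorded reason and the allocated treatment of that period are the main evidence available.

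**Working it through.** **1. Does any planned analysis compare stopping for muscle symptoms by treatment?**

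| Planned analysis | Split by treatment? | Split by reason? |
|---|---|---|
| Reasons for withdrawal (SAP 2.3.7) | No, overall | Yes |
| Description of withdrawal and adherence (2.3.7) | Yes | Not stated |
| Period of first known withdrawal (2.3.7) | Yes | No |
| Adherence models (2.3.7) | Yes | No |
| Safety tables (2.3.3) | Yes | Events not collected |
| VAS, any symptoms, attributed symptoms, impact scores (2.3.1, 2.3.2) | Yes | Symptoms, not stopping |

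On the safety row: Protocol 2.11 limits reporting to events meeting the serious criteria, and its adverse event definition leaves out events listed in the SmPC. The SmPC (Appendix 8, section 4.8) lists myalgia as common. Non-serious muscle symptoms that lead to stopping therefore do not reach these tables.

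**2. How many exits does the plan allow for?** Protocol 2.4 states: "A sample size of 64 participants provides approximately 90% power to detect a treatment effect of at least 10mm". It then allows for 40% loss to follow-up: 64 / (1 - 0.40) = 106.7, so 107, which reproduces the protocol's figure. Applied to the final 200, the allowance is 0.40 × 200 = 80. This covers loss to follow-up in general. The form separates lost patients from early withdrawals, and only the latter have a coded reason, so 80 is best read as an upper figure for withdrawals.

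**3. Dilution.** Let N be the number of withdrawals, m those for muscle symptoms, f = m/N, and p the share of the m that fall in statin periods. With three statin and three placebo periods in random order, the null share is 0.5. If the other withdrawals split 50:50 (an assumption), the all-cause statin share is 0.5 + f(p - 0.5). For m = 30 and p = 0.75:

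- N = 80: 0.5 + 0.375 × 0.25 = 0.594
- N = 40: 0.5 + 0.750 × 0.25 = 0.688
- N = 35: 0.5 + 0.857 × 0.25 = 0.714

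**4. Power.** The SAP names no test for this comparison. I assume an exact two-sided binomial test against 0.5 at the SAP's 5% level. The all-cause count is the sum of Bin(m, p) and Bin(N - m, 0.5); the muscle-specific count is Bin(m, p). The documents give no split by cause, so m and p are assumptions shown over a range.

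| N | m | p | All-cause share | Power, all-cause | Power, muscle-specific |
|---|---|---|---|---|---|
| 80 | 30 | 0.75 | 59% | 32% | 80% |
| 40 | 30 | 0.75 | 69% | 64% | 80% |
| 35 | 30 | 0.75 | 71% | 72% | 80% |
| 80 | 40 | 0.80 | 65% | 73% | 98% |
| 60 | 30 | 0.80 | 65% | 56% | 94% |
| 60 | 15 | 0.70 | 55% | 7% | 30% |
| 80 | 30 | 0.60 | 54% | 7% | 18% |
| 20 | 5 | 0.75 | 56% | 7% | 0% |

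In the last row the muscle-specific test cannot reach 5%: its smallest two-sided p-value is 2 × 0.5^5 = 0.0625.

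**The case against.** A reader might infer that muscle symptoms, as a known harm, are never compared by treatment. The documents do not support that. Daily VAS muscle symptom score is the primary outcome, and any muscle symptoms, symptoms attributed to the medication and impact scores are all compared in SAP 2.3.2. Whether statins cause these symptoms is the trial's question (SAP 1.6), so calling them a known harm presupposes the answer.

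It is also tempting to say that the worst-affected patients simply disappear. Protocol 2.10.4 allows a patient to stop for one period and resume at the next, and asks those who stop, even permanently, to keep submitting outcome data for the current period. SAP 1.10 analyses by allocation irrespective of adherence, and SAP 2.3.4 plans missing-not-at-random scenarios. Only patients without VAS data on both treatments drop out of the primary set.

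Other objections carry weight:

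- SAP 2.3.7 already relates withdrawal to statin and placebo periods descriptively, and a table by reason would fit under that sentence. But the one sentence that mentions reasons says overall, so the split is not promised.
- Treating the whole 40% allowance as withdrawals exaggerates the dilution; at 40 or 35 withdrawals the loss of power is much smaller.
- The muscle-specific comparison is not always the more powerful, as the case of 5 events in 20 shows.
- A 50:50 split of other withdrawals is an assumption: withdrawals for clinical concern or other drug effects need not balance.
- All-cause withdrawal is robust to misstated reasons, so it should not be displaced.

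**Conclusion.** The gap is real but narrow. Withdrawal or stopping because of muscle symptoms is recorded on two forms, is not compared by treatment in SAP 2.3.7, and is not caught by the safety tables. No primary conclusion and no stated figure changes; this is an inexpensive improvement to an exploratory secondary analysis.

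The gain cannot be fixed from the documents. With 30 muscle withdrawals at 75% on statin and a 50:50 split elsewhere, power is 80% for the muscle-specific comparison, against 32% all-cause at 80 withdrawals, 64% at 40 and 72% at 35. At a 60% statin share, or with a handful of events, neither comparison tells the reader much. The case for tabulating reasons by treatment does not rest on power: without it, a reader cannot see whether muscle-symptom withdrawals were equal or unequal between treatments.

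**What to change.** In SAP 2.3.7, before database lock:

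1. **Table.** Tabulate the B.3 reasons for withdrawal and the Q2 reasons for not taking study medication by the treatment allocated in that period. For withdrawals, use the rule already in 2.3.7, under which a withdrawal between periods is assigned to the period just ended.
2. **One added comparison.** Alongside the all-cause comparison, not in place of it, pre-specify a statin-placebo comparison of each patient's first withdrawal or stopping because of muscle symptoms (B.3b or either Q2 muscle option). Use one fixed method, for example the statin share of first events with an exact 99% confidence interval, the SAP's level for secondary outcomes. Present it as an estimate, with no switch of method according to the event count.
3. **Stated limits.** Q2 opens only for the two lowest adherence answers, so a late stop reported as taking medication on most days is missed. Patients lost to follow-up have no coded reason.

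The cost is a few lines of text, one table and one estimate. No new data, form or visit is needed, and no clinical rule changes. SAP section 1 allows changes until the plan is finalised before lock. The downside is one more exploratory comparison, resting on a reason stated by the patient or clinician under blinding.

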2.3.8 CHANGES FROM TRIAL PROTOCOL

In the original protocol, the primary analysis model was exactly as above, but with fixed period effects in addition. These fixed effects have been removed, due to a strong belief that the clinical situation makes it unlikely for period effects to occur. The primary analysis model specified in the original protocol will be undertaken as a sensitivity analysis, as detailed in Section 2.3.4.

The original protocol did not mention one of the secondary analyses, which sets the primary outcome measure to zero if the patient attributes the symptoms to another cause (Section 2.3.2). This analysis was added after the protocol was finalised, but was included in the published protocol paper.
